2.3.1 Cardiovascular events

ions thereof. In the 39-week dog toxicity study, subtle cardiac microscopic findings, consisting of minimal valvular inflammatory cell infiltration, or minimal to slight epithelial inflammation/fibroplasia of the epicardium in the right atrium, were seen in the heart of one-third of treated dogs without 10 dose relationship. Findings were subtle, minor, focal, and not associated with any changes in systemic cardiovascular parameters. They were not seen in any dog study of shorter duration These findings did not cause any biological or clinical consequences in the animals in this study and were thus not considered to be adverse. These findings were not seen in the 13-week dog study. This conclusion was supported after comprehensive review of the data by 5 nonclinical pathologists (including a cardiovascular expert pathologist). Additionally, external advice on the potential human implications was sought from a British Heart Foundation Professor of Cardiology. It was concluded that short-term exposure should not lead to any relevant abnormality or clinical disease, and even with long-term exposure the potential hazard and likelihood of an adverse pericardial or valvular effect in humans is extremely low. Echocardiographic monitoring of study participants in the Phase 2 proof of concept study (EP0069) and its open-label extension (EP0073) was undertaken, and no major findings have been observed to date.

Despite the occurrence of ECG findings such as ectopies (asymptomatic, not requiring clinical intervention), there are no current data suggesting that PSL has an adverse effect on cardiovascular function other than a minimal lowering effect on BP. The degrees of reduction of both SBP and DBP are consistent with the GABA_A-targeted mechanism of action of PSL and do not appear likely to have a clinically significant effect in the apeutic use. As a precaution from preclinical and clinical findings of nonclinically significant ECG abnormalities and hypotension, ECGs and vitals are being assessed frequently in current clinical studies.

Psychiatric events 2.3.2

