^e This is only done for study participants taking OX prior to the morning dose of OXC. If the study par At the Screening Visit, the blood sample must be c	C. If the study participant administers OXC in the morning ticipant administers OXC once daily, then the blood sample collected no later than on Day -7 (with MHD reassessment, or later than Day - 2	and evening, the blood sample should be obtained e should be obtained just prior to the daily dose. if required, no later than Day -4); other safety
f A serum pregnancy test will be performed at Scree EOS/FT for women of childbearing potential only	sning for women of childlearing potential only. A urine pre-	gnancy test will be performed at Baseline and at
^g Triplicate 12-lead ECGs and vital signs (after a recollection prior to the morning dose of PSL.	st of at least 5 minutes at 2, to 3-minute intervals) will be pe	erformed on Days 1 through 12, prior to the PK
^h Triplicate 12-lead ECG (after a rest of at least 5 m points at Day 8: predose, 0.5h, 1h, 2h, 3h, 6h, and triplicate 12-lead ECGs will be performed after a r 0.5h, 1h, 2h, 3h, and 6h postdose for the morning a	inutes at 2- to 3-minute intervals) will be taken shortly prior 12h post the morning dose of PSL. In addition, 1 day prior test of at least 5 minutes at 2- to 3-minute intervals for each administration of PSL, and 0.5h predose for the evening administration of PSL.	r to each of the following PK collection time to the first dose of PSL on Day -1 (Baseline) of the following matching time points: predose, ministration of PSL, where dosing time is
equivalent to the expected time of dosing on Day 8 Investigational medicinal product will be administ	s. ered bio 12h apart each day. All study participants enrolled	into the study will receive 1 day of PSL at
100mg bid (Day 1) followed by 2 further days at 2 and once on Day 8 in the morning. A dose taper we PSL 200mg. Padsevonil 200mg bid will be admini	Uting bid (Day 2 and Day 3). Padsevonil 400mg will then the bill be initiated on the evening of Day 8, when study particip stered on Day 9 and Day 10. Padsevonil 100mg bid will be	be administered orally bid on Day 4 through Day 7 bants will be administered an evening dose of administered on Day 11 and Day 12.

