10.7.1 Physical examination

Full physical examinations will be performed at the time points specified in Table 5-1. Full physical examinations will include cardiac and respiratory function via auscultation and review of the following body systems: general appearance; ear, nose, and throat; eyes; hair and skin; respiratory; cardiovascular; gastrointestinal; musculoskeletal; hepatic; neurological; and mental status.

Height (study participant without shoes, and height rounded to the nearest 0.5cm) and body weight (study participant in underwear or light clothing, without shoes and rounded to the nearest 0.1kg) will be recorded at the Screening Visit and BMI will be derived (weight (kg)/ [height (m)]²).

Vital signs

his docuration vit Vital signs (PR, RR, SBP, DBP, and oral temperature) will be recorded at the time points shown in Table 5-1.

For the purposes of assessing the inclusion criterion, at the Screening Visit and the Baseline Visit, BP measurements will be performed in both supine and standing positions according to the following procedure: Measure supine BP after the study participant has been lying down for 10 minutes, then ask the study participant to stand up and record the standing BP variations thereof. after 1 minute and 3 minutes. At all time points after the Baseline Visit, BP will only be measured in the supine position, ie, there will be no assessment for orthostatic hypotension.

By decision of the sponsor and the Investigator, the time points specified in Table 5-1 may be modified based on preliminary safety and PK assessments from previous doses tested in the study.

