10.7.3 Standard 12-lead ECG

Triplicate standard 12-lead ECGs (RR interval, PR interval, QRS interval, QT, QTcB, and QTcF) will be recorded at times specified in Table 5-1, according to the following procedure: study participant lies in a supine position for >5 minutes; then a 12-lead ECG wilk be recorded in the same position. All ECG recordings will be performed in triplicate at 2- to 3 minute intervals.

Electrocardiograms will be recorded at a speed of 25mm/s and with a calibration of 1cm/mV.

The purpose of the enhanced ECG monitoring procedures in this study is to match the observed ECG parameters with the contemporaneous plasma levels of PSL as closely as possible, at key time points during Day -1 (no exposure) and Day 8 (anticipated peak exposure). This will support an evaluation of any relationship between exposure to PSL and changes in key ECG parameters, most particularly QT intervals.

As specified in Table 5-1, a Baseline ECG series will be performed on Day -1. On this day, triplicate standard 12-lead ECGs will be performed for each of the following time points, intended to match as closely as possible the timing of the PK sampling series planned for Day 8: 0h, 30min, 1h, 2h, 3h, 6h and the pre-evening dose PK sample. On Day 8, a matching series of ECGs will be performed predose, 30min, 1h, 2h, 3h, and 6h after the morning dose of PSL, and approximately 30min before the evening dose, as close as possible to the time of the pre-evening dose PK sample. On Day 1 through Day 12, except Day 8, the triplicate standard 12-lead ECG will be performed prior to the morning dose of PSL, again timed to match as closely as possible to the time of the predose PK sample being taken. Care should be taken to record the timing of each ECG and PK sample as accurately as possible, to enable the precise evaluation of their temporal relationship.

By decision of the sponsor and the Investigator, the time points specified in Table 5-1 may be modified based on preliminary safety and PK assessments from the study.

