Urinalysis of	Specific gravity, pH, glucose, protein, blood, leukocytes, nitrite, ketones, bilirubin, urobilinogen (with dipstick)
At Cant.	If protein, blood, or leukocytes are abnormal (positive), a microscopic examination of the sediment will be performed.
Drug screen	Amphetamines/methamphetamines, benzodiazepines, barbiturates, cocaine, cannabis, methadone, tricyclic antidepressants and opiates

Padsevonil

Laboratory assessment	Parameters
-----------------------	------------

ALP=alkaline phosphatase; ALT=alanine aminotransferase; AST=aspartate aminotransferase; HBsAG=hepatitis B surface antigen; HCV-Ab=hepatitis C antibody; HIV-1/2Ab=human immunodeficiency virus-1/2 antibodies; SFU=Safety Follow-Up

^a Shift tables will be presented for these variables

Vital signs, physical findings, and other observations related to other safety Vital signs 10.4

vital signs
The following vital signs measurements will be obtained with the study participants resting in the supine position for 10 minutes at all timepoint after the Baseline Visit:
Systolic and diastolic blood process. tion and any extensio

- Pulse rate
- Oral body temperature
- Respiratory rate

A by- participant listing of all vital sign measurements and change from Baseline will be presented by treatment group and timepoint.

Descriptive statistics will be reported for all vital sign measurements. Measured values and changes from Baseline will be summarized by vital signs variables and timepoint for each treatment group.

The number and percentage of study participants with treatment-emergent markedly abnormal (TEMA)/potentially clinically significant (PCS) vital sign values as calculated by the criteria outlined in Table 10–2 will be summarized by treatment group at each timepoint.

Table 10-2:	TEMA/PCS	criteria for	vital signs
-------------	----------	--------------	-------------

Variable	Unit of	Low ^a	High ^a
Systolic blood pressure	mmHg	Value <90 and ≥20 decrease from Baseline	Value >140 and ≥20 increase from Baseline
Diastolic blood pressure	mmHg	Value <50 and ≥15 decrease from Baseline	Value >90 and ≥15 increase from Baseline
Pulse rate	bpm	Value <45 and ≥15 decrease from Baseline	Value >90 and ≥15 increase from Baseline

bpm=beats per minute; PCS=potentially clinically significant; TEMA=treatment-emergent markedly abnormal. ^a Both conditions must be satisfied for a measurement to be considered potentially clinically significant.

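### All scheduled on-drug blood pressure readings fall about 12 h after a dose, so the planned summaries can miss a post-dose fall

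*Protocol*

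**What the plan says.** **Timing of vital signs.** Protocol Table 5-1, footnote g, covers ECGs and vital signs together. The text copy splits the footnote into "Triplicate 12-lead ECGs and vital signs (after a recollection prior to the morning dose of PSL" and "erformed on Days 1 through 12, prior to the PK". Read in order, it places both before the predose PK sample on each of Days 1 to 12, and Day 8 is not excepted. Doses are 12 h apart (footnote i).

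**Timing of ECGs.** Footnote h gives the enhanced series, "points at Day 8: predose, 0.5h, 1h, 2h, 3h, 6h, and" 12 h, with matching times on Day -1. It names the ECG only. Section 8.2.2.2 likewise gives Day 8 clock times for ECGs and lists vital signs without any. Section 10.7.3 explains the purpose: ECGs are matched to plasma levels on Day -1 (no exposure) and on "Day 8 (anticipated peak exposure").

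**Why blood pressure is watched.** Section 2.2 reports small, transient reductions in blood pressure that resolved by themselves. Section 2.3.1 treats a minimal pressure-lowering effect as the one cardiovascular effect suggested by the data, and says that, as a precaution, "ECGs and vitals are being assessed frequently in current clinical studies".

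**Analysis.** Protocol Section 12.4.3 and SAP Table 3-1 give vital signs a single baseline (Day 1 predose) and give ECGs a time-matched Day -1 baseline. SAP Section 10.4.1 states that "Descriptive statistics will be reported for all vital sign measurements". It also counts participants meeting Table 10-2 (for low SBP: below 90 mmHg and a fall of at least 20 mmHg) by group at each timepoint. SAP Section 4.3 keeps unscheduled and repeated values after the first dose out of the descriptive statistics.

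**The concern.** The protocol gives two reasons for close cardiovascular monitoring: minor ECG abnormalities and hypotension. It answers the first with readings spread over the Day 8 dosing interval. The second is covered only by readings at the end of an interval.

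If a transient fall in pressure follows each dose and fades before the next one, the plan has no scheduled reading at the time it occurs. The change-from-baseline table could then look flat, and the low-SBP and low-DBP rows of Table 10-2 could be empty, without showing that pressure was stable after dosing. At stake is the interpretation of a safety summary: a null result would describe trough only.

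**Working it through.** The plan states no figure on this point to reproduce. The check is a count of scheduled readings, followed by two illustrations on assumed values.

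**1. Scheduled readings against doses**

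Inputs: Protocol Table 7-1 (doses); Table 5-1 footnotes g and i; Section 8.3.1 and the notes to Table 5-1 (Day 13 vital signs before morning discharge).

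- Doses: 12 days × 2 = 24. Of these, 4 × 2 + 1 = 9 are 400 mg.
- Vital-sign sets on Days 1 to 12: 12. The Day 1 set precedes any drug and is the baseline, leaving 12 − 1 = 11 on drug. Day 13 adds one more, also about 12 h after the last dose.

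| Vital signs on | Preceding evening dose | Sets |
|---|---|---|
| Day 2 | 100 mg | 1 |
| Days 3, 4 | 200 mg | 2 |
| Days 5, 6, 7, 8 | 400 mg | 4 |
| Days 9, 10, 11 | 200 mg | 3 |
| Days 12, 13 | 100 mg | 2 |

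Total 12 sets, each about 12 h after a dose. Scheduled vital signs between a morning dose and the next evening predose time: 0.

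**2. Day 8, side by side**

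| Time | ECG | Vital signs |
|---|---|---|
| Predose | yes | yes |
| 0.5, 1, 2, 3, 6 h | yes (5 times) | none scheduled |
| Before evening dose (about 12 h) | yes | none scheduled |

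The last row is itself a trough, so the gap is the five times from 0.5 to 6 h.

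**3. How far 12 h is from peak (assumed values)**

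The documents give no half-life and no tmax. With mono-exponential decline after the peak, level at 12 h ÷ peak = 2^(−(12 − tmax)/t½).

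| Assumed t½ | tmax 1 h | tmax 3 h |
|---|---|---|
| 3 h | 2^(−11/3) = 0.079 | 2^(−9/3) = 0.125 |
| 6 h | 2^(−11/6) = 0.281 | 2^(−9/6) = 0.354 |
| 12 h | 2^(−11/12) = 0.530 | 2^(−9/12) = 0.595 |

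The range is about 8% to 60% of peak. It is too wide to say how much is lost.

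**4. What that could do to the summaries (assumed values)**

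Assume SBP with mean 120 mmHg, between-subject SD 11, within-subject SD 7, a baseline of 90 to 145 mmHg (inclusion criterion 9), and an effect proportional to concentration. If the fall at peak is Δ and a fraction f remains at the reading, the mean change shown is f × Δ. For Δ = 15 mmHg, that is 15 at peak, 7.5 at f = 0.5 and 3.75 at f = 0.25.

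The Table 10-2 low-SBP probability is P(V < 90 and B − V ≥ 20), where B is the baseline and V the later reading. By simulation (400,000 draws), the expected count per 14 participants for one reading is:

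| Fall at peak | f = 1 | f = 0.5 | f = 0.25 |
|---|---|---|---|
| 10 mmHg | 0.35 | 0.10 | 0.05 |
| 15 mmHg | 14 × 0.0701 = 0.98 | 14 × 0.0137 = 0.19 | 14 × 0.0050 = 0.07 |
| 20 mmHg | 2.26 | 0.35 | 0.10 |

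These figures show direction and rough scale only.

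**The case against.** **The effect is small, and its timing is not described.** The protocol calls the pressure reductions minor and of no clinical consequence. Transient is not tied to hours after a dose; Section 2.2 describes adverse events in general as easing over the first days of dosing. If blood pressure behaves that way, daily predose readings are not obviously badly timed. This stands. A reader might infer that hypotension will be missed, or that the effect is known to follow concentration; the documents say neither.

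**The counts may be near zero either way.** In the illustration, a true fall of 10 mmHg gives 0.35 expected cases per 14 even when measured at peak. This stands too. The clearer gain is in the change from baseline and the lowest post-dose value.

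**There are other safeguards.** Participants are in the unit from the afternoon of Day 7 to Day 13, adverse events are prompted at each visit, unscheduled vital signs are allowed and would be listed, and Section 10.7.2 lets time points be modified. These help with symptomatic events. They do not put post-dose readings into the summaries: SAP Section 4.3 excludes unscheduled values, and the option to modify time points is not a plan to do so.

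**Two further inferences are not part of this point.** One is that dropping standing measurements is an oversight. Section 10.7.2 states the choice openly: "At all time points after the Baseline Visit, BP will only be measured in the supine position". The other is that a comparison of the two groups is compromised. Blood pressure is summarised descriptively by group, and no comparative inference on it is planned.

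**Conclusion.** The gap is real and modest. All 12 scheduled on-drug vital-sign sets (11 on Days 2 to 12, plus Day 13) come about 12 h after a dose, four of them after 400 mg, and none accompanies the five Day 8 ECGs at 0.5 to 6 h. That part rests on the schedule alone.

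The consequence is conditional: the summaries and Table 10-2 counts can miss a post-dose fall. Its size cannot be fixed from the documents, because it depends on half-life, tmax and the relation of pressure to concentration. The 8% to 60% range is an assumption-based bracket.

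Changes in vital signs belong to the other safety variables, ranked below the incidence of adverse events. The primary PK comparison is untouched. This is a worthwhile, cheap improvement to a safety summary.

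**What to change.** - **Protocol Table 5-1 (footnotes g and h) and Sections 8.1.2, 8.2.2.2 and 10.7.2:** record supine SBP and DBP at the existing Day 8 ECG times and the matching Day -1 ECG times. Pulse rate is optional, since the ECG already supplies heart rate. Place the readings so that they do not disturb the PK sampling windows.
- **Protocol Section 12.4.3 and SAP Table 3-1:** let these Day 8 readings use the time-matched Day -1 baseline, and keep the Day 1 predose baseline for other days. Without this, the new readings would conflict with the current baseline definition.
- **SAP Section 10.4.1 and Table 10-2:** include the new time points in the summaries and counts, and show the lowest post-dose value per participant.

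**Cost:** up to seven additional cuff readings on each of two days, plus a protocol and SAP amendment. The participant is already supine for the ECG, and no visit or blood draw is added. The early Day 8 times are busy, with triplicate ECGs, venous draws and MITRA samples inside ±5 min windows, so the order of procedures needs to be written down.

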5.8 Schematic diagram

The study schematic diagram for UP0070 is presented in Figure 5-1.

Figure 5-1: Schematic diagram

N=28 total study participants

**

#

- trough sample before first and after last dose of Padsevonil
- Last dose of Padsevonil 400mg in the morning
- After morning Padsevorit 400mg dose on Day 8

bid=twice daily; BRV=brivaracetam; LEV=levetiracetam; LTG=lamotrigine; OXC=oxcarbazepine PK=pharmacokinetic(s); PSL=Padsevonil; SFU=Safety Follow-Up; T=Titration

Rationale for study design and selection of dose 5.9

In an earlier study (UP0002), carbamazepine (CBZ, a strong CYP3A4 inducer) was demonstrated to reduce PSL exposure by >80% compared with a control group where coadministration of non-inducing AED drugs (LEV/LTG) had no impact on PSL exposure. Oxcarbazepine is a known CYP3A4 inducer with less potency compared with CBZ (Andreasen et al, 2007). The primary objective of this study is to evaluate the effect of stable coadministered OXC on the PK of repeated doses of PSL 400mg bid in study participants with epilepsy, compared with study participants co-medicated with stable doses of LEV, LTG, or BRV therapy.

(the maximum intended therapeutic c mosure), which demonstrates no safety concerns in the patient popula comparison with previous studies performed with this dose (UP0002). The PSL dose will be 400mg bid (the maximum intended therapeutic dose and hence highest exposure), which demonstrates no safety concerns in the patient population and provides a

SELECTION AND WITHDRAWAL OF STUDY 6 PARTICIPANTS

6.1 Inclusion criteria

To be eligible to participate in this study, all of the following criteria must be met:

- ations thereof. 1. An Independent Ethics Committee (IEC) approved written ICF is signed and dated by the study participant.
- 2. Study participant is considered reliable and capable of adhering to the protocol (eg, able to understand and complete diaries), visit schedule, and medication intake according to the judgment of the Investigator.
- 3. Study participant is male or female between 18 to 64 years of age, inclusive, with a diagnosis of epilepsy according to the International League Against Epilepsy (ILAE) classification (Fisher et al, 2014).
- 4. Study participant is currently treated for epilepsy with stable doses of the following for at least 3 months:
 - a) Inducers Group: OXC (at least 1200mg/day as monotherapy or in combination with BRV [up to 200mg/day], LEV [at least 1g/day] or LTG [at least 150mg/day]); or
 - b) Neutral (control) Group: LTG (at least 150mg/day monotherapy or adjunctive to LEV or BRV), LEV (at least 1g/day monotherapy or adjunctive to LTG), or BRV (up to 200mg/day adjunctive to LTG).
- 5. Study participant in the Inducers Group is taking OXC and has a trough OXC metabolite (MHD) plasma level in the target range (≥ 12.0 to ≤ 35.0 mcg/mL). At the Screening Visit, the blood sample must be collected no later than on Day -7 (with MHD reassessment, if required, no later than Day -4).
- 6. Study participant is in generally good physical and mental health, in the opinion of the Investigator, determined on the basis of medical history and a general clinical examination at the Screening Visit (ie, study participant has no current or past medical history of clinical significance, other than epilepsy, that would mitigate against their participation in the study).
- 7. Study participant has clinical laboratory test results within the local reference ranges or values are considered as not clinically relevant by the Investigator and approved by the UCB Study Physician. Laboratory parameters outside the reference ranges can be retested and if the retest result is within the reference range or considered as clinically not relevant the study participant is allowed in the study. Alanine aminotransferase (ALT), aspartate aminotransferase (AST), or alkaline phosphatase (ALP) should be within the normal limits. Liver enzymes up to 25% above the upper limit may be repeated once and should be within normal limits before inclusion.
- 8. Study participant has a body mass index (BMI) of 18 to 35kg/m², inclusive, with a body weight of at least 50kg (male) or 45kg (female).
- hisdocul 9. Study participant has BP and PR within normal range in the supine position after 5 minutes rest (SBP: 90mmHg to 145mmHg, DBP: 40mmHg to 95mmHg, PR: 40bpm to 100bpm).

thereo

Any values outside the normal range, but considered not clinically significant by the Investigator, are allowed.

10. Female study participant has a negative serum pregnancy test at the Screening Visit and agrees to use an efficient form of contraception for the duration of the study (unless menopausal [defined as no menses for 12 months without an alternative medical cause]; a high follicle-stimulating hormone level in the postmenopausal range may be used to confirm a postmenopausal state in women not using hormonal contraception or hormonal replacement therapy). Hormonal contraception may be susceptible to an interaction with the IMP, which may reduce the efficacy of the contraception method. The potential for reduced efficacy of any hormonal contraception methods requires that a barrier method (preferably male) condom) also be used.

Birth control methods considered as an efficient form of contraception:

- Combined (oestrogen and progestogen containing) hormonal contraception (oral, implant, or injectable) associated with inhibition of ovulation in combination with a barrier method (preferably male condom)
- Progestogen-only hormonal contraception associated with mhibition of ovulation in combination with a barrier method (preferably male condom)
- Intrauterine device (IUD)
- Intrauterine hormone-releasing system (IUS) in combination with a barrier method (preferably male condom)
- Bilateral tubal occlusion
- Vasectomized partner
- Sexual abstinence

True abstinence is an acceptable form of contraception when this is in line with the preferred and usual lifestyle of the person. Periodic abstinence (eg, calendar ovulation, symptothermal, postovulation methods), declaration of abstinence for the duration of the study, and withdrawal are not acceptable methods of contraception.

- Progestogen-only oral hormonal contraception, where inhibition of ovulation is not the primary mode of action in combination with a barrier method (preferably male condom)
- Male or female condom with spermicide (ie, double barrier)
- Cap, diaphragm, or sponge with spermicide

To ensure proper birth control, females who use hormonal contraception should use an efficient barrier contraceptive in the 3 months following the end of the study (ie, for 3 months after the last intake of study medication).

This documen 11. Male study participant agrees that, during the study period, when having sexual intercourse with a woman of childbearing potential, he will use an efficient barrier contraceptive (condom plus spermicide) AND that the respective partner will use an additional efficient contraceptive method (eg, oral pills, IUDs, IUSs, or diaphragm, and spermicide).

6.2 **Exclusion criteria**

Study participants are not permitted to enroll in the study if any of the following criteria is met:

- 1. Study participant has previously received the IMP administered in this study.
- ationsthereof 2. Study participant has participated in another study of an investigational medication (or a medical device) within the last 3 months before screening (or 5 half-lives, whichever is longer) or is currently participating in another study of an investigational medication (or a medical device).
- 3. Study participant has a known hypersensitivity to any components of the IMP as stated in this protocol
- 4. Study participant has a current or past psychiatric condition that, in the opinion of the Investigator, could compromise his/her safety or ability to participate in this study or a history of schizophrenia, or other psychotic disorder, bipolar disorder, or severe unipolar depression. The presence of potential psychiatric exclusion criteria will be determined based on the psychiatric history collected at the Screening Visit.
- 5. Study participant has a lifetime history of suicide attempt (including an actual attempt, interrupted attempt, or aborted attempt), or has had suicidal deation in the past 6 months as indicated by a positive response ("Yes") to either Question 4 or Question 5 of the "Screening/Baseline" version of the C-SSRS at the Baseline Visit.
- 6. Study participant has any medical condition that, in the opinion of the Investigator, could jeopardize or would compromise the study participant's ability to participate in this study.
- 7. Study participant has a history of status epilepticus during the last year.
- 8. Study participant has a history or presence of drug or alcohol dependency or tests positive for alcohol and/or drugs at the Screening Visit or Day -1.
- 9. Study participant has a consumption of more than 3 units of alcohol/day in case of females, more than 4 units of alcohol/day in case of males.
- 10. Study participant smokes more than 5 cigarettes per day (or equivalent) or has done so within 6 months prior to the Screening Visit.
- 11. Study participant has a consumption of more than 600mg of caffeine/day within 7 days prior to the Baseline Visit and does not agree to limit consumption below this limit for the duration of the study 200mL of coffee contains approximately 100mg of caffeine, 200mL of black tea approximately 30mg, and 200mL of cola approximately 20mg).
- Juit of col Juit ingests grapefruit, starfrui within 72 hours before first administration c Treatment Period and throughout the study. 12. Study participant ingests grapefruit, starfruit, or pawpaw (as beverage, fruit, or supplements) within 72 hours before first administration of IMP. These fruits are not allowed during the

Padsevonil

variations thereof.

13. Study participant has either:

- >2.0x upper limit of normal (ULN) of any of the following:
 - 0 ALT
 - AST 0
 - ALP 0

-OR-

ULN total bilirubin (\geq 1.5xULN total bilirubin if known Gilbert's syndrome).

If study participant has elevations only in total bilirubin that are >ULN and <1.5xULN, fractionate bilirubin to identify possible undiagnosed Gilbert's syndrome (ie, direct bilirubin <35%).

For randomized study participant with a baseline result >ULN for ALT, AST, ALP, or total bilirubin, a baseline diagnosis and/or the cause of any clinically meaningful elevation must be understood and recorded.

If study participant has >ULN ALT, AST, or ALP that does not meet the exclusion limit at screening, repeat the tests, if possible, prior to dosing to ensure there is no further ongoing clinically relevant increase. In case of a clinically relevant increase, inclusion of the study participant must be discussed with the UCB Study Physician.

Tests that result in ALT, AST, or ALP up to 25% above the exclusion limit may be repeated once for confirmation. If out of range again, the study participant cannot be included.

- 14. Study participant has made a blood or plasma donation or has had a comparable blood loss (>400mL) within the last 3 months prior to the Screening Visit.
- 15. Study participant has a history or present condition of respiratory or cardiovascular disorders, eg, cardiac insufficiency, coronary heart disease, hypertension, arrhythmia, tachyarrhythmia, or myocardial infarction.
- 16. Study participant has any clinically relevant ECG finding at the Screening Visit or at Baseline. Study participant has an abnormality in the 12-lead ECG that, in the opinion of the Investigator, increases the risks associated with participating in the study. In addition, any study participant with any of the following findings will be excluded: (a) QT interval corrected for heart rate using Bazett's formula (QTcB) or Fridericia's formula (QTcF) >450ms in 2 of 3 ECG recordings; (b) other conduction abnormalities (defined as PR interval \geq 220ms), (c) irregular rhythms other than sinus arrhythmia or occasional, rare supraventricular or rare ventricular ectopic beats. In case of an out of range result, 1 repeat will be allowed. If out of range again, the study participant cannot be included.
- 12. Study participant has a history of unexplained syncope or a family history of sudden death due to long OT syndrome.
- This docut 18. Study participant tests positive for human immunodeficiency virus-1/2 antibody (HIV-1/2Ab), hepatitis B surface antigen (HBsAg), or hepatitis C antibody (HCV-Ab).
 - 19. Female study participant tests positive for pregnancy, plans to get pregnant during the participation in the study, or is breastfeeding.

20. Study participant has received any prescription or nonprescription medicines, including enzyme inhibitors or inducers, over the counter (OTC) remedies, herbal and dietary orvariationsthereof supplements (including St. John's Wort), or vitamins up to 2 weeks or 5 half-lives of the respective drug (whichever is longer) before the first administration of IMP and during the clinical part of the study, unless required to treat an AE. This does not include allowed AEDs per the protocol, oral contraceptives not exceeding 30µg ethinyl estradiol or postmenopausal hormone replacement therapy or implants, patches, or IUDs/IUSs delivering progesterone (for female study participants).

